8.6.2. Sample Size Consideration

Considering that Flixotide is an established brand, which has been in the China market for more than 10 years, it is more sensible to consider drug related AE (adverse drug reaction, ADR) instead of any specific rare case.

Based on global phase III studies FAS30007 [GlaxoSmithKline Document Number [GM2001/00151/00](#)], FAS30030 [GlaxoSmithKline Document Number [RM2004/0187/00](#)] and FAS30009 [GlaxoSmithKline Report Number [GM2001/00103/00](#)] on 1 to <4 years old, the smallest incidence rate of ADR in a given study was 3%. The Japanese post market safety survey reported the ADR rate as 1.68%. Taken the lowest estimate between two approaches, assuming the ADR rate in Chinese 1 to <4 year old children patients is not lower than 1.5%, it is calculated that a study with 150 subjects will have approximately 90% probability to observe at least one ADR.

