8.6.4. Key Elements of Analysis Plan

Safety Analysis

Safety data will be summarized and/or listed for the safety population.

The duration of exposure to Flixotide 50 μ g will be summarized and patient medical history will be listed.

Concomitant medication will be coded using WHO drug and will be summarized by Anatomical Therapeutic Chemical (ATC) classification.

AEs will be coded using MedDRA, and grouped by body system. AEs occurring during administration of Flixotide 50 μ g will be summarized. The number and percentage of subjects experiencing at least one AE of any type, AEs within each body system and AEs within each preferred term will be presented. Separate summaries will be provided for all AEs, drug related AEs, SAEs, and for AEs leading treatment discontinuation.

Analysis methods

No formal hypothesis will be tested in this study. AEs will be listed and summarized descriptively to provide frequency estimate of ADR (=incidence rate of any drug related AEs in safety population) and frequency estimates for any other adverse events reported.

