10.1.1. Time Period and Frequency for Collecting AE and SAE information

- The investigator or site staff is responsible for detecting, documenting and reporting events that meet the definition of an AE or SAE.
- SAEs will be recorded from the time the consent form is signed through Visit 3; AEs will be recorded from the start of Flixotide 50 µg treatment through Visit 3.
- Investigators will assess causality within 24 hours. Once the investigator determines that an AE/SAE is identified as explicitly attributed to any GSK product (including products not covered in the specific study objective), the investigator must report the ADR to Vendor and GSK China within 5 calendar days upon awareness. All SAEs will be recorded and reported to GSK within 24 hours of awareness. GSK standard AE and SAE Collection Forms ([Appendix 1](#), [Appendix 2](#)) will be used to collect safety information. GSK China will forward the information to GCSP following internal process.
- Investigators are not obligated to actively seek AEs or SAEs in former study subjects. However, if the investigator learns of any SAE, including a death, at any time after a subject has been discharged from the study, and he/she considers the event reasonably related to the study treatment or study participation, the investigator must promptly notify GSK.

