Relationship to GSK Product(s)	
It is a regulatory requirement for investigators to assess relationship to GSK product(s) based on information available. The assessment should be reviewed on receipt of any new information and amended if necessary. 'A reasonable possibility' is meant to convey that there are facts/evidence or arguments to suggest a causal relationship. Facts/evidence or arguments that may support 'a reasonable possibility' include, e.g., a temporal relationship, a pharmacologically-predicted event, or positive dechallenge or rechallenge. Confounding factors, such as concomitant medication, a concurrent illness, or relevant medical history, should also be considered.
 
Note: If the event is related to the use of a GSK Product the ADR pages must be completed.

--------------------------------	--

IDSL Version 07.02 - 26 APR 16 [AE]

CONFIDENTIAL

Protocol Identifier	Subject Identifier	
_____	_____	

NON-SERIOUS ADVERSE EVENTS (AE)

Note: If this is a Serious Adverse Event (SAE), do not complete this form, go to the SAE section and complete the SAE form.

Note: If this Adverse Event (AE) is related to the GSK Product(s), complete both this AE form AND the Adverse Drug Reaction (ADR) form.

Did the subject experience any non-serious adverse events during the study? Yes No If Yes, record details below.

Event Diagnosis Only (if known) Otherwise Sign/Symptom	Start Date Day Month Year	Start Time Hr : Min 00:00-23:59	Outcome 1=Recovered/ Resolved 2=Recovering/ Resolving 3=Not recovered/ Not resolved 4=Recovered/ Resolved with sequelae	End Date Day Month Year	End Time Hr : Min 00:00-23:59	Maximum Intensity 1=Mild 2=Moderate 3=Severe X=Not appli- cable	Action Taken with GSK Product(s) as a Result of the Non-serious AE 1=GSK product(s) withdrawn 2=Dose reduced 3=Dose increased 4=Dose not changed 5=Dose interrupted/ Delayed X=Not applicable	With- drawal Y=Yes ¹ N=No	Rela- tionship to GSK Product(s) Y=Yes ² N=No
e.g., Headache	26 JAN 12	13:25	1	27 JAN 12	10:20	1	4	N	N
1.		:			:				
2.		:			:				
3.		:			:				
4.		:			:				

¹ Complete Study Conclusion page and Adverse event as reason for withdrawal. ²The ADR pages should be completed only if this question is answered Yes.

CONFIDENTIAL

**ADVERSE DRUG REACTION (ADR)
INVESTIGATOR INSTRUCTIONS**

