SECTION 3 If GSK Product(s) was Stopped, Did the Reported Event(s) Recur After Further GSK Product(s) Were Administered?	If deliberate or inadvertent administration of further dose(s) of GSK product(s) to the subject occurred, did the reported adverse event recur?
---	---

IDBL Version 07.02 - 26 APR 18 [AE]

CONFIDENTIAL

Protocol Identifier	Subject Identifier	
		

ADVERSE DRUG REACTION (ADR)

SECTION 1 Event Details

Use this section to record adverse drug reactions which are clinically or temporally related. If adverse drug reactions are not clinically or temporally related, use a new ADR form for this subject.

Row Number	Event Details (As reported on the AE Form)	Start Date
		Day Month Year

SECTION 2 Demography Data

For GSK use only

Enter the subject's year of birth.

Year of birth  Year	Imputed date of birth PPD  Day  Month  Year	Sex  Male Weight  .  kg Height  .  cm  Female
---	---	--

SECTION 3 If GSK Product(s) was Stopped, Did the Reported Event(s) Recur After Further GSK Product(s) were Administered?

Yes No Unknown at this time Not applicable

SECTION 4 Possible Causes of ADR Other Than GSK Product(s). all that apply:

 Disease under study	 Concomitant medication(s) specify _____
 Lack of efficacy	 Medical condition(s) specify _____
 Withdrawal of GSK product(s)	 Other, specify _____
 Transmission of an infectious agent via a medicinal product	

CONFIDENTIAL

**ADVERSE DRUG REACTION (ADR)
INVESTIGATOR INSTRUCTIONS**

SECTION 7	Complete this section using the information in the GSK Product page. Details of all GSK product(s) which may have caused the AE should be included. Provide specific details in Section 9 Adverse Drug Reaction summary if the subject has taken an overdose of GSK product(s), including whether it was accidental or intentional.
Details of GSK Product(s)	IDBL Version 07.02 - 28 APR 16 [AE]

CONFIDENTIAL

Protocol Identifier	Subject Identifier	
		

ADVERSE DRUG REACTION (ADR) (Continued)

SECTION 5 RELEVANT Medical Conditions

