Most Clinically Significant Action Taken with Study Treatment(s) as a Result of the SAE	Indicate the response to the adverse event, whether it be from the investigator, local physician not in the study, or the subject. Study treatment(s) withdrawn = Administration of study treatment(s) was permanently discontinued. Dose reduced = Dose is reduced for one or more study treatment(s). Dose increased = Dose increased for one or more study treatment(s). Dose not changed = Study treatment(s) continues even though an adverse event has occurred. Dose interrupted/Delayed = Administration of one or more study treatment(s) was stopped/interrupted temporarily but then restarted. Not applicable = Subject was not receiving study treatment(s) when the event occurred (e.g., pre- or post-dosing) or the subject died and there was no prior decision to discontinue Study Treatment(s).

IDSL Version 06.03 - 07 MAY 14 [SAE with Intensity_InForm]

CONFIDENTIAL

SERIOUS ADVERSE EVENTS (SAE) (Page 4 of 6)
INVESTIGATOR INSTRUCTIONS

Did the subject withdraw from the study as a result of this SAE	Indicate 'Yes' if the event(s) were directly responsible for the subject's withdrawal from the study, otherwise indicate 'No'.
Relationship to Study Treatment(s)	It is a regulatory requirement for investigators to assess relationship to study treatment(s) based on information available. The assessment should be reviewed on receipt of any new information and amended if necessary. 'A reasonable possibility' is meant to convey that there are facts/evidence or arguments to suggest a causal relationship. Facts/evidence or arguments that may support 'a reasonable possibility' include, e.g., a temporal relationship, a pharmacologically-predicted event, or positive dechallenge or rechallenge. Confounding factors, such as concomitant medication, a concurrent illness, or relevant medical history, should also be considered.

IDSL Version 06.03 - 07 MAY 14 [SAE with Intensity_InForm]

CONFIDENTIAL

Protocol Identifier	Subject Identifier	Centre Number	Randomisation Number	
_____	_____	_____	_____	_____

SERIOUS ADVERSE EVENT (SAE)

Did the subject experience a serious adverse event during the study? [Y]  Yes [N]  No If Yes, record details below.										
SECTION 1										

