Event	Start Date	Start Time	Outcome	End date	End Time	Maximum Intensity	Most Clinically Significant Action Taken with Study Treatment(s) as a Result of the SAE	Withdrawal	Relationship to Study Treatment(s)	
Diagnosis Only (if known) Otherwise Sign/Symptom	Day Month Year	Hr : Min 00:00-23:59	1=Recovered/Resolved 2=Recovering/Resolving 3=Not recovered/ Not resolved 4=Recovered/ Resolved with sequelae 5=Fatal	If fatal, record date of death.	Day Month Year	Hr : Min 00:00-23:59	1=Mild 2=Moderate 3=Severe X=Not applicable	1=Study Treatment(s) withdrawn 2=Dose reduced 3=Dose increased 4=Dose not changed 5=Dose interrupted/Delayed X=Not applicable	Did the subject withdraw from study as a result of this SAE?	Is there a reasonable possibility the SAE may have been caused by the study treatment?
e.g., Anaphylaxis	25 JAN 10	13:25	1	27 JAN 10	10:20	1	4	Y	Y	
		:			:					
		:			:					

* Complete Study Conclusion page and ✓ Adverse event as reason for withdrawal.

SECTION 2 Seriousness (specify reason(s) for considering this a SAE, ✓ all that apply:									
[A]  Results in death	[B]  Results in disability/incapacity	[C]  Possible drug-induced liver injury (see definition in SAE section of the protocol)							
[B]  Is life-threatening	[E]  Congenital anomaly/birth defect								
[C]  Requires hospitalisation or prolongation of existing hospitalisation	[F]  Other, specify _____ (see definition of SAE)								

CONFIDENTIAL

SERIOUS ADVERSE EVENTS (SAE) (Page 5 of 6)
INVESTIGATOR INSTRUCTIONS

SECTION 4 If Study Treatment was Stopped, Did the Reported Event(s) Recur After Further Study Treatment(s) Were Administered?	If deliberate or inadvertent administration of further dose(s) of study treatment(s) to the subject occurred, did the reported adverse event recur?
--	---

IDS Version 06.03 - 07 MAY 14 [SAE with Intensity_InForm]

CONFIDENTIAL

Protocol Identifier	Subject Identifier	
		

SERIOUS ADVERSE EVENT (SAE) (Continued)

SECTION 3 Demography Data	For GSK use only Enter the subject's year of birth.		
Year of birth  Year	Imputed date of birth PPD Day  Month  Year	Sex  Male  Female	Weight  kg Height  cm

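### Does section 8.6.4 need to say which drug the adverse drug reaction (ADR) frequency refers to?

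*Combined protocol and SAP*

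**What the plan says.** Section 7 sets the objective as the post-marketing safety profile of Flixotide 50 µg in children aged 1 to <4 years. Its first primary goal is the incidence of known adverse reactions.

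Section 8.6.2 explains the sample size in a sentence that opens with Flixotide's time on the Chinese market and concludes that "it is more sensible to consider drug related AE (adverse drug reaction, ADR) instead of any specific rare case". Section 8.6.4 uses the same equation of ADR with drug related AE for the analysis: the "frequency estimate of ADR (=incidence rate of any drug related AEs in safety population").

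Three other places word relatedness differently:

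- Section 10.1.1 covers an event "attributed to any GSK product (including products not covered in the specific study objective), the investigator must report the ADR" within a set number of days.
- The non-serious AE form in Appendix 1 says that, for an event "related to the GSK Product(s), complete both this AE form AND the Adverse Drug Reaction (ADR) form". It excludes serious events: "If this is a Serious Adverse Event (SAE), do not complete this form".
- The SAE form in Appendix 2 instructs that "It is a regulatory requirement for investigators to assess relationship to study treatment(s) based on information available", and its causality item asks: "Is there a reasonable possibility the SAE may have been caused by the study treatment".

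The instructions for Section 7 of the ADR form add: "Details of all GSK product(s) which may have caused the AE should be included".

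**The concern.** The ADR frequency is the quantity on which the study is sized, and few subjects are expected to contribute to it, so its numerator should be unambiguous. Section 8.6.4 defines it without naming the drug. Its reference to AEs occurring while Flixotide is being given limits timing, not attribution.

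The forms seem to carry the ambiguity into the data. The non-serious AE form has one Yes/No relationship item covering GSK products in general. The SAE form asks about study treatment, a term that an observational protocol has little reason to use and that this one does not define. A program that counted every Yes across the two forms would put two scopes into one numerator, and the plan does not say how the forms are to be combined. At stake is whether the reported rate describes Flixotide 50 µg or that product together with anything else from the same sponsor.

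**Working it through.** **1. The plan's own figure.** Inputs from section 8.6.2: n = 150 and an ADR rate of 1.5%.

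- P(at least one ADR) = 1 − (1 − 0.015)^150 = 0.896, against about 90% stated. The figure reproduces.
- At the two source rates in the same section, the probability is 0.921 (1.68%, the Japanese survey) and 0.990 (3%, the smallest phase III rate).
- The source rates come from phase III studies of fluticasone propionate and from the Japanese survey, cited in a passage about Flixotide. The calculation is therefore naturally about Flixotide, and reading section 8.6.4 the same way leaves it unchanged.

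**2. The texts side by side.**

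- Section 7: the objective names Flixotide 50 µg only.
- Section 8.6.2: ADR is equated with drug related AE, with Flixotide the only drug under discussion.
- Section 8.6.3: the safety population is defined by at least one dose of Flixotide 50 µg.
- Section 8.6.4: exposure to Flixotide 50 µg is summarised, AEs are those arising while it is given, and the 8.6.2 equation is repeated. No other product is named anywhere in 8.6.
- Section 10.1.1: the wider scope sits in a rule on who reports, to whom and by when. Its parenthesis describes the other products as not covered by the study objective. The analysis in 8.6.4 serves that objective.
- Appendices 1 and 2: section 10.1.1 calls these the sponsor's standard forms. The SAE form has a field for a randomisation number and asks whether the treatment blind was broken; neither applies to a single-arm observational study. Differences in wording between such templates are weak evidence that two analysis scopes were intended.

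**3. Can the narrow reading be carried out?** For SAEs, the item already asks about study treatment, which here can only sensibly be Flixotide 50 µg. For non-serious events, a Yes leads to the ADR pages, and Section 7 there lists the suspected product or products.

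There is one limit. An ADR form may hold several clinically or temporally related reactions, and Section 7 lists products by form, not by event. A form with two products and two events would need case review. At the planning rate, 150 × 0.015 = 2.25 subjects with an ADR are expected, so reading each case is feasible.

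**4. Size if the wide scope were used by mistake.**

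- One extra subject adds 1/150 = 0.67 percentage points. For example, 2/150 = 1.33% (exact 95% CI 0.16 to 4.73) becomes 3/150 = 2.00% (0.41 to 5.73). The intervals overlap almost entirely.
- The documents give no ADR rate for other GSK products. Purely as an assumption, take an independent extra incidence q. The pooled rate is 1 − (1 − 0.015)(1 − q). For q = 0.5%, 1% and 2% it is 1.99%, 2.49% and 3.47%, or 2.99, 3.73 and 5.21 expected subjects in 150. Nothing in the documents supports any of these values of q.
- Serious events: section 6.1 reports no SAE attributable to fluticasone among 703 treated subjects. The exact two-sided upper 95% limit is 1 − 0.025^(1/703) = 0.523%, and 150 × 0.00523 = 0.79 subjects. This is an upper confidence limit on an expected count, not a maximum, and it carries over a rate from studies of 12 or 52 weeks. It indicates that the SAE wording matters little.

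**The case for a change.** The strongest case for a change is that the rule should not be left to the analyst. The relationship flag on the non-serious AE form cannot by itself isolate Flixotide. The look-up in Section 7 of the ADR form is nowhere mentioned in the analysis plan. Concomitant asthma medication is expected and collected, so exposure to another GSK product cannot be ruled out from the text. The programme is a regulatory requirement, very few ADRs are expected, and one clarifying sentence would cost almost nothing.

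The factual parts stand: section 8.6.4 names no drug, the forms use different terms, and no rule for combining them is written. The step from there to a likely error does not. A wrong count needs a child on another GSK product, an event during Flixotide treatment attributed only to that other product, no Flixotide ADR in the same child, and an analyst who disregards both the objective and the product list on the ADR form. The documents name no other GSK product as given to these children; the one that appears on the forms is a form-filling example.

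Nor would an automatic rule based on Section 7 be clearly better than judgement, because that section does not link products to individual events.

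**Conclusion.** The concern identifies missing detail, not a fault. Read with section 7 and the rest of section 8.6, drug related in section 8.6.4 means related to Flixotide 50 µg, and the existing forms allow that count, with case review where one ADR form lists several products. The wider scope in section 10.1.1 works as a reporting rule and need not match the analysis.

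No stated figure is wrong: 89.6% agrees with about 90%. A single misclassified subject would move the rate by 0.67 percentage points, but how often that would occur cannot be derived from the documents. The study tests no hypothesis, so no decision turns on it.

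This rests on two assumptions: that study treatment on the SAE form means Flixotide 50 µg, and that the analyst follows the stated objective when deriving the count. Both are the natural reading. No change to the plan is called for.

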8.7. Quality control and Quality Assurance

In accordance with applicable regulations, applicable standards for the conduct of observational studies, and GSK procedures, monitors will contact the site prior to the inclusion of the first subject to review with the site staff the protocol, program requirements, and their responsibilities to satisfy regulatory, ethical, and GSK requirements.

The sites will be monitored to ensure that the:

- Subjects included in the program are authentic.
- Safety and rights of subjects are being protected.
- The program is conducted in accordance with the currently approved protocol and any other program agreements, applicable standards for the conduct of observational studies, and all applicable regulatory requirements.

The investigator and the head of the medical institution (where applicable) agrees to allow the monitor access to all relevant documents in accordance with applicable standards for the conduct of observational studies.

To ensure compliance with applicable standards for the conduct of observational studies and all applicable regulatory requirements, GSK may conduct a quality assurance audit of the site records, and the regulatory agencies may conduct a regulatory inspection at any time during or after completion of the program.

In the event of an audit or inspection, the investigator (and institution) must agree to grant the auditor(s) and inspector(s) direct access to all relevant documents and to allocate their time and the time of their staff to discuss any findings/relevant issues.

8.8. Limitations of the research methods

8.8.1. Study closure/uninterpretability of results

- Upon completion or premature discontinuation of the study, the GSK monitor will conduct site closure activities with the investigator or site staff, as appropriate, in accordance with applicable regulations including GCP, and GSK Standard Operating Procedures.
- GSK reserves the right to temporarily suspend or prematurely discontinue this study at any time for reasons including, but not limited to, safety or ethical issues or severe non-compliance. For multicenter studies, this can occur at one or more or at all sites.

- If GSK determines such action is needed, GSK will discuss the reasons for taking such action with the investigator or the head of the medical institution (where applicable). When feasible, GSK will provide advance notification to the investigator or the head of the medical institution, where applicable, of the impending action.
- If the study is suspended or prematurely discontinued for safety reasons, GSK will promptly inform all investigators, heads of the medical institutions (where applicable) and/or institution(s) conducting the study. GSK will also promptly inform the relevant regulatory authorities of the suspension or premature discontinuation of the study and the reason(s) for the action.
- If required by applicable regulations, the investigator or the head of the medical institution (where applicable) must inform the Institutional Review Board (IRB)/Independent Ethics Committee (IEC) promptly and provide the reason for the suspension or premature discontinuation.

8.9. Other aspects

None.

9. PROTECTION OF HUMAN SUBJECTS

9.1. Ethical approval and subject consent

The study will be conducted in accordance with all applicable regulatory requirements, and with GSK policy.

The study will also be conducted in accordance with International Conference on Harmonisation (ICH) Good Clinical Practice (GCP), all applicable subject privacy requirements, and the guiding principles of the current version of the Declaration of Helsinki. This includes, but is not limited to, the following:

- IRB/IEC review and favorable opinion/approval of the study protocol and amendments as applicable
- Signed informed consent must be obtained for each subject (from their parent/guardian) before participation in the study (and for amendments as applicable)
- Investigator reporting requirements (e.g. reporting of AEs/SAEs/protocol deviations to IRB/IEC)
- GSK will provide full details of the above procedures, either verbally, in writing, or both.

